Protocol for validating the clinical effect of a knee brace

Presented to the Véritas IRB Research Ethics Committee

TOPMED

Version 02

Approved in French on May 8th 2024

Translated on August 6th 2025

NCT06655558

SCHEDULED START AND END DATES

December 2023 to December 2024

RESEARCH PROJECT DESCRIPTION

Issues

Knee orthoses are one form of treatment for patients suffering from gonarthrosis. The aim of this form of treatment is to compensate for certain biomechanical deficits in patients. A multitude of joint arrangements are available to target specific biomechanical deficits. A constant challenge for orthosis manufacturers is to transmit the biomechanical effect of the orthosis to the patient. The desired effect requires a change in the forces applied inside the knee, but the orthosis cannot directly transmit the forces to the patient's bones due to its external nature. Orthotic customization is essential to improve the transmission and tolerance of the biomechanical effect. O3D Inc. is keen to validate the effectiveness of its new custom orthosis in treating symptoms.

State of knowledge and project relevance

The changing demographics of the Canadian population are playing an important role in the growing need for orthopaedic devices. The aging population is constantly on the rise, partly due to increasing life expectancy [1-3]. At the same time, chronic diseases of the musculoskeletal system (e.g. osteoarthritis), whose prevalence increases with age, are limiting the daily activities of sufferers, affecting more and more people [4]. Osteoarthritis is the most common form of these diseases worldwide [5]. According to the Institut de la statistique du Québec, nearly one in two Quebecers aged 15 and over suffers from a chronic health problem [6-8]. Furthermore, Statistics Canada informs us that "in 2016, 20.6% of Canadians aged 15 and over reported having been diagnosed with arthritis by a health professional" [9]. The knee is one of the critical joints in the practice of activities of daily living (ADLs). Knee orthoses are a way of helping people with gonarthrosis to carry out their daily activities.

The effectiveness of orthotic treatment can be measured by a reduction in gonarthrosis symptoms or medication intake, and potentially an increase in the patient's ability to perform problematic movements. As the orthoses will be custom-made, we wish to explore the relationship between orthotic efficacy and patient anthropometry. The Western Ontario and McMaster Universities Osteoarthritis Index Questionnaire (WOMAC) is a scientifically validated tool for measuring pain, stiffness and ability to perform tasks of daily living in gonarthrosis. This tool is used regularly with this type of patient to measure the evolution of their symptoms during various types of intervention.

Research objectives

The aim of this research is to validate the clinical effect of a custom-made orthosis.

With this research, we seek to answer the following questions:

- Does this new orthosis help control the symptoms of gonarthrosis?
- Does the participants' anthropometry influence the control of gonarthrosis symptoms?

Our hypotheses are that treatment with the new orthosis will reduce patients' symptoms. We have no hypotheses regarding a potential relationship between anthropometry and treatment efficacy.

Financing

The project was funded by NSERC's *Strengthening College and Community Innovation* program in partnership with O3D Inc.

Partner company

O3D Inc.

[name], President

[name]

[contact]

[contact]

RESEARCH METHODOLOGY

Research location

On TOPMED's premises at Collège Mérici, [name].

Type of test

Measurements will be taken using a single-group repeated measures methodology: before and after an 8-week intervention.

Measurement, assessment and data collection tools

Questionnaires :

A questionnaire containing general information: age, gender, height, weight and brace-wearing history. This questionnaire will only be completed prior to the start of treatment.

A Quebec version of the Western Ontario and McMaster Universities Osteoarthritis Index (WOMAC) questionnaire will be used to quantify the evolution of the participant's symptoms and their effects on quality of life. This questionnaire will be completed twice (before and after the treatment phase).

Anthropometric measurements :

The anthropometric measurements used by O3D to make the participant's orthosis will be transmitted to the research team. These data will be used in analyses to explore relationships with treatment efficacy.

Estimated duration of participants' activities

Questionnaire

Two questionnaires must be completed before starting treatment with the custom-made orthosis (total duration approx. 18 minutes). **Participants who have already begun treatment will no longer be eligible for the study.** After 8 weeks of treatment, a questionnaire will have to be completed again (duration approx. 15 minutes). For each questionnaire, a link will be sent to the participant by e-mail so that he or she can access it on the Lime Survey platform (accessible on the Internet).

INVOLVEMENT OF LIVE HUMAN, ANIMAL OR MATERIAL PARTICIPANTS

50 adult participants will be recruited. Participants must have gonarthrosis. Only participants who receive a regular model of the O3D orthosis will be able to take part.

Participant inclusion criteria:

- Medial gonarthrosis;
- Be between the ages of 18 and 75 inclusively;
- Receive a regular model of the O3D orthosis

Participant exclusion criteria:

- Tri-compartmental gonarthrosis
- Have completed the delivery meeting for your O3D orthosis

SCIENTIFIC JUSTIFICATION FOR USING LIVE SUBJECTS

The participation of human participants representative of the clientele is essential for validating the efficacy of treatment with the custom-made orthosis. The evolution of the participants' symptoms will give us essential information on the efficacy of the orthosis, and relationships can be explored between it and their anthropometric measurements.

RECRUITMENT

Potential candidates will receive information about the research project and a link to the study page on our website when they visit us for impressions to make a regular model of an O3D orthosis. Candidates must register their interest via our website. The information and consent form will be sent to the e-mail address provided. The research team will be available to answer any questions candidates may have ([contact]), assess eligibility, send documentation and/or set up a telephone appointment at a later date.

RISKS AND DRAWBACKS, AND PROPOSED MITIGATION MEASURES

An allergic skin reaction (redness) due to wearing the brace is a potential injury. The participant should stop wearing the brace, if necessary.

Bruises, corns, scratches and/or pain may appear on the braced limb, due to improper fitting of the brace or incorrect positioning of the brace. Injuries due to brace breakage are also possible.

ADVANTAGES AND BENEFITS

No immediate benefit for participants, except the benefit of trying a new orthosis that could improve their quality of life. The advantage of their participation is that it will provide empirical data on orthosis wear. This is an advantage for O3D Inc.

FREE AND INFORMED CONSENT

The Lime Survey link containing the Information and Consent Form (ICF) will be e-mailed to them once they have shown interest. A delay of one (1) week will be allowed for reading and reflection. In order to participate in the study, participants must have completed the first questionnaire before the orthosis delivery date.

Participants may terminate their participation at any time without negative consequences or prejudice and without having to justify their decision. In this case, participants must inform the responsible researcher or a member of the research team. Thereafter, all material allowing the identification of the participant and the data provided will be destroyed, unless the participant authorizes the researcher to use them for research purposes despite the withdrawal. In this case, the information will be retained as described below and will be applied to all other participants.

CONFIDENTIALITY AND PROTECTION OF PERSONAL INFORMATION

The information collected in the questionnaires and anthropometric measurements is confidential and will be used only for the purposes of this research project, unless otherwise agreed by the participant. All data collected, notes and computer records are encrypted on servers. Unless required by law, no information that could directly or indirectly reveal your identity will be disseminated or published without your prior explicit consent.

All digital questionnaires have been created using the Lime Survey platform. The processed information is hosted in Canada on the platform's encrypted servers (Secure Socket Layer procedure), which comply with the RGPD standard.

Data will be stored in coded form for a period of five (5) years, then anonymized in a database for retention for a period of ten (10) years for statistical reference purposes.

CONTINUOUS EXAMINATION

Should any inconvenience arise during or as a result of the research project, participants will be promptly notified.

DISSEMINATING RESULTS

No disclosure to patients will be made following the trials.

A scientific publication of the results is planned.

COMPENSATION

No compensation will be offered for participation in this study.

RESPONSIBILITY

The legal rights of each participant will be maintained.

PROTOCOL SEQUENCE

First contact

Demonstration of the participant's interest by answering via the TOPMED website's research page.

Admission

Sending documents and explanations :

- *0241_03DA_CourrielFIC* (contains link to FIC and online questionnaire)
- *0241_03DA_CourrielQuest* (contains link to online questionnaire)

Receipt of signed consent and questionnaire

Receiving anthropometric measurements

8-week lead time

Final questionnaire sent

Data processing

Data recording: Questionnaires and anthropometric measurements

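### The protocol sets out to validate the orthosis's effect, but one group measured before and after 8 weeks can only show a change in WOMAC, and no attribution limit is stated

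*Protocol*

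**What the plan says.** **Design.** Under Research Methodology, Type of test: "Measurements will be taken using a single-group repeated measures methodology: before and after an 8-week intervention". The section on measurement tools has the WOMAC filled in twice, once on each side of the treatment phase. Fifty adults are to be recruited. The protocol describes no control or waiting-list group, no repeated baseline, no period without the brace and no external benchmark.

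**Claim.** The title is "Protocol for validating the clinical effect of a knee brace". Under Research objectives: "The aim of this research is to validate the clinical effect of a custom-made orthosis", and the first question is "Does this new orthosis help control the symptoms of gonarthrosis". The hypothesis there is that treatment with the orthosis will lower symptoms. The section justifying the use of live subjects says that human participants are needed to validate the efficacy of the treatment, and that the course of their symptoms is key information on that efficacy. The background section puts the inference in general form: "The effectiveness of orthotic treatment can be measured by a reduction in gonarthrosis symptoms or medication intake".

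**Secondary interest.** On body measurements, "we wish to explore the relationship between orthotic efficacy and patient anthropometry"; the protocol declares no hypothesis for this.

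**Reporting.** A scientific publication is planned. No section says that the change may be due to anything other than the orthosis.

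**The concern.** The aim is causal and the contrast is not. A causal reading needs some account of what WOMAC would have been after 8 weeks without the orthosis, and the protocol collects nothing that supplies one. A statistical analysis plan could not repair this, because the protocol itself fixes both the objective and the data.

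At stake is the conclusion. If the trial runs as written and WOMAC falls significantly, the protocol's own wording leads straight to the statement that the orthosis has been validated. The same result could arise with an orthosis that does nothing. A larger sample would not help, since the bias does not shrink with n.

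**Working it through.** **Step 1: what the contrast contains.** The only available contrast is mean WOMAC before minus mean WOMAC after, in the same people. Its expected value is

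orthosis effect + placebo response + natural course + co-treatment + regression to the mean.

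- *Placebo response:* WOMAC is self-reported by people who know that they wear a new custom brace.
- *Natural course:* symptoms can vary over 8 weeks, and no untreated group shows by how much.
- *Co-treatment:* the protocol states no rule on it. Medication intake is named in the background as a possible measure of effectiveness, but no listed tool records it. The general questionnaire is described as covering age, gender, height, weight and brace history; the WOMAC covers pain, stiffness and daily tasks.
- *Regression to the mean:* possible, because candidates are approached when they come for brace impressions. It adds to the fall only if they enter at a transient peak that lasts to the baseline WOMAC. No WOMAC entry threshold is set, so its size is unknown.

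That is one observed difference and five unknown terms. The anthropometry analysis lies within the same group and supplies no counterfactual.

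**Step 2: illustration of scale.** The protocol gives no test, alpha, SD, correlation or loss rate, so there is no stated figure to reproduce. Only n = 50 comes from the document. Assumed: two-sided 5% paired t-test, all 50 analysed, true orthosis effect zero, pre-post correlation r from 0.5 to 0.9, and a mean fall f (in baseline SD) from non-orthosis causes.

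- SD of change = √(2(1 − r)), in baseline SD units
- Noncentrality = f / √(2(1 − r)) × √50
- Probability of a significant fall = P(T > 2.0096), with T noncentral t on 49 df

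Worked case, f = 0.20 and r = 0.8: SD of change = √0.4 = 0.632; 0.20 / 0.632 = 0.316; 0.316 × √50 = 2.236; probability = 0.592.

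| f (baseline SD) | r = 0.5 | r = 0.7 | r = 0.8 | r = 0.9 |
|---|---|---|---|---|
| 0 | 2.5% | 2.5% | 2.5% | 2.5% |
| 0.05 | 5.3% | 6.5% | 7.9% | 11.8% |
| 0.10 | 10% | 14% | 19% | 34% |
| 0.20 | 28% | 43% | 59% | 87% |
| 0.30 | 55% | 77% | 91% | 99.6% |

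If 40 were analysed (20% loss assumed), the 0.20 row becomes 23%, 36%, 50% and 79%.

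**Step 3: reading.** The result depends almost wholly on f, which the document does not give. The table shows that the problem can be anything from slight to total. It does not estimate where this trial lies.

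**The case against.** The strongest reply is that the design is openly declared, that a causal question may motivate a weak design, and that the limit belongs on the conclusion, which nobody has yet drawn. Some of the text is indeed modest: WOMAC is said to quantify how symptoms evolve, and the orthosis is said only to be capable of improving quality of life. The document is also a translation from French, so single words should not be pressed. Much of this stands, and it is why the remedy is confined to the aim, the justification and the conclusion. It does not remove the point: the causal sense is the same in the title, aim, question, hypothesis and justification, and the limit appears nowhere.

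A reader might infer more than the document supports:

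- *That a single group is itself an error.* It is not. It is sound for describing change.
- *That medication was not recorded.* The protocol lists no tool for it, but the questionnaire is only summarised, so what was collected is unknown. The background sentence names medication as one possible measure and does not commit the trial to it.
- *That every causal phrase is a study claim.* "O3D Inc. is keen to validate the effectiveness of its new custom orthosis in treating symptoms" reports the partner company's wish.
- *That the anthropometry question is a second overclaim of the same weight.* It is already exploratory and has no hypothesis.
- *That the percentages are this trial's false-positive risk.* They are conditional on assumed inputs.

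**Conclusion.** The point holds as a mismatch between objective and design. The trial can estimate the change in WOMAC during 8 weeks of orthosis use. It cannot validate effect, effectiveness or efficacy, and the protocol does not say so. This conclusion rests on the document alone and needs none of the assumed figures.

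Its size cannot be fixed. Under the stated assumptions, the probability of a significant improvement with a useless orthosis is 2.5% if nothing else changes and runs from about 5% to nearly 100% for non-orthosis falls of 0.05 to 0.30 baseline SD. The data remain usable for description. The fault is correctable and should be corrected before the results are published.

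**What to change.** 1. Restate the aim, the justification for human participants and the conclusion of the planned publication as: *to estimate the change in WOMAC over 8 weeks of orthosis use, without a concurrent control*. Add that the change cannot be attributed to the orthosis.
2. Report any anthropometry result as an association with change in WOMAC.
3. If no tool outside the protocol's list captured medication and other co-treatment, state this as a limitation. If one did, report what it shows.

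**Cost.** Wording only, with no new data, visits or participants. It can still be done in the publication after the scheduled period, "December 2023 to December 2024". The downside is a weaker claim than the partner company wants.

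A concurrent control is not asked for, as it would be a different trial. For scale, splitting the 50 participants 25/25 would give two-sided 5% power of about 18%, 42% or 81% for assumed between-group effects of 0.3, 0.5 or 0.8 SD.

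### The baseline WOMAC must come before brace delivery but may be of any age, so symptom change while the brace is being made counts as brace effect

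*Protocol*

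**What the plan says.** *Design.* Under Type of test, the protocol describes one group measured before and after an 8-week intervention. There is no control group.

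*Which forms, and when.* Under Measurement, assessment and data collection tools, there is a general-information form: "This questionnaire will only be completed prior to the start of treatment". There is also the WOMAC: "This questionnaire will be completed twice (before and after the treatment phase".

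*Latest time for the baseline.* Under Estimated duration of participants' activities: "Two questionnaires must be completed before starting treatment with the custom-made orthosis", about 18 minutes in total. The same paragraph adds "Participants who have already begun treatment will no longer be eligible for the study". The exclusion criteria also remove anyone whose delivery meeting has taken place.

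*Condition for taking part.* Under Free and informed consent: "participants must have completed the first questionnaire before the orthosis delivery date". The form is singular and not named.

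*Operational steps.* Under Protocol sequence, Admission lists two e-mails. The first "contains link to FIC and online questionnaire"; the second links to an online questionnaire only. The next step is "Receipt of signed consent and questionnaire", again singular. Receipt of the anthropometric measurements, an 8-week wait and the final questionnaire follow. Brace delivery is not a listed step.

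*Point of contact.* Under Recruitment, candidates learn of the study when they attend for the impressions from which the brace is made.

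**The concern.** The result of this trial is the final WOMAC minus the baseline WOMAC. With no control group, nothing in the design separates the brace from whatever else changes symptoms between the two measurements. The length and placing of that interval therefore matter more than they would in a randomised trial.

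The protocol closes the interval at one end only. A participant who answers soon after the impressions visit and one who answers the day before delivery both comply, yet their baselines describe different states. People tend to seek a brace when symptoms are troublesome, and scores taken at such a time tend to ease by themselves. Others may worsen while they wait. The first kind of change inflates the apparent effect and the second hides part of it. If the gap also varies between participants, it adds spread to the change scores that the anthropometry analysis tries to explain.

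A second, smaller matter is that the consent section and the Protocol sequence speak of one questionnaire where the activities section requires two.

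**Working it through.** The protocol gives no figure for this gap, so there is none to reproduce. The check compares the timing statements, with a little arithmetic.

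**Step 1. Is the baseline WOMAC covered by the latest limit?** The two starting forms take about 18 minutes together. The form repeated after 8 weeks takes about 15. The general-information form is completed once only, so the repeated form is the WOMAC. The remainder is 18 − 15 = 3 minutes, which fits a short form on age, gender, height, weight and brace history. The two forms due before treatment therefore include the WOMAC, and its latest limit is the start of treatment.

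**Step 2. Is there an earliest limit?** The statements that bear on it are:

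- Recruitment: first contact is at the impressions visit.
- Free and informed consent: one week is allowed for reading and reflection once the consent link is sent; the questionnaire must be done before delivery.
- Protocol sequence: consent and questionnaire are received, then measurements; neither step is dated relative to delivery.

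None says how old the baseline may be at delivery. The permitted range runs from shortly after the impressions visit up to delivery.

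**Step 3. What does the gap do to the estimate?** Let B be the baseline score, D the score the participant would have given on the day of delivery, and F the final score. Then

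F − B = (D − B) + (F − D).

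The second term covers the 8 weeks of treatment. The first is untreated change over a gap of g weeks. The planned comparison reports the sum, so the error from the gap equals the mean of D − B. It is zero only if symptoms are stable on average while the brace is made.

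**Step 4. How large is it?** Neither g nor the mean of D − B is given. As an illustration only, assumed gaps of 2 to 8 weeks would place the two WOMACs 8 + 2 = 10 to 8 + 8 = 16 weeks apart. With a limit of 7 days, they would be at most 8 + 1 = 9 weeks apart if the final form is answered at 8 weeks of treatment.

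**Step 5. Do the sections agree on the number of forms?** The activities section requires two. The consent section requires the first, unnamed. The Protocol sequence sends two links and waits for one form. Taken as the baseline round, in contrast to the final questionnaire, the consent wording agrees with the activities section. Taken as the form in the first e-mail, it is looser. The text does not settle which is meant.

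**The case against.** The strongest reply is that pre-treatment drift is a limitation of every single-group before-after study, and that baseline windows are often left to a statistical analysis plan, which is not shown here. Both statements are fair. However, an analysis plan can only choose among scores that were collected. If no second WOMAC is requested before delivery, the missing score cannot be recovered later, so the step belongs among the data-collection rules. The 7-day figure is an example; another limit fixed in advance would serve.

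Three stronger readings are tempting and are not supported.

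- *The baseline may follow the start of brace wear.* A reader might infer this from the consent section taken alone. The measurement section places the WOMAC before treatment, the activities section requires both forms by then, and anyone who has begun treatment is ineligible. A late baseline would breach the protocol.
- *The trial loses power through late baselines.* Any such figure would need an assumed share of late forms, an assumed part of the effect already present and an assumed effect size. The protocol gives none of these, and the calculation would describe a breach of the plan.
- *The before-after interval exceeds a stated 8 weeks.* The 8 weeks is the length of treatment. The protocol states no interval between the two questionnaires that could be exceeded.

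The text is also a translation, so the singular in the consent section is weak evidence of intent. That part supports a wording change and no more.

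**Conclusion.** The point stands in a limited form. The baseline WOMAC has a latest limit and no earliest one. In a design without a control, untreated change between the baseline and delivery is attributed to the brace. This follows from the text on either reading of the consent sentence.

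Its size is unknown, and its direction depends on whether symptoms ease or worsen during the wait. It would be negligible if braces were delivered within days of the impressions or if symptoms were stable over that time; the protocol shows neither. A tighter baseline would not remove untreated change during the 8 weeks of treatment, which the single-group design leaves in the result.

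This is a cheap improvement to the data collection. The difference in wording between the sections is a secondary point of alignment.

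**What to change.** 1. Obtain each participant's delivery date from O3D and keep it with the submission date of each questionnaire.
2. Set in advance a maximum age for the baseline WOMAC at delivery, for example 7 days. Where the score is older, re-send the Lime Survey link before the delivery meeting.
3. Use the latest pre-delivery score as baseline. If the repeat is not returned in time, keep the first score and report its age.
4. Report the change between the two pre-delivery scores as a check on drift, with the gap in days.
5. In Free and informed consent, require both the general-information questionnaire and the baseline WOMAC before the delivery meeting. In Protocol sequence, make the receipt step plural and add delivery as a step. This also shows where the 8 weeks begins: the sequence lists it after receipt of measurements, while the activities section counts weeks of treatment, and the two should be reconciled.

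The cost is one date per participant, a few sentences in the protocol, and a repeated online form of about 15 minutes for some of the 50 participants.

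### Does destroying the data of participants who withdraw, unless they authorise its use, damage the planned before-after analysis?

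*Protocol*

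**What the plan says.** All of the withdrawal rule stands in the Protocol under Free and informed consent.

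- The right: "Participants may terminate their participation at any time", with no reason needed.
- The trigger: "participants must inform the responsible researcher or a member of the research team". Not answering the final questionnaire does not set the rule in motion.
- The default: "all material allowing the identification of the participant and the data provided will be destroyed".
- The exception: "unless the participant authorizes the researcher to use them for research purposes despite the withdrawal". Data kept on this ground are then held on the same terms as everyone else's.

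Three other places bear on it. Under Confidentiality and protection of personal information: "Data will be stored in coded form for a period of five (5) years, then anonymized in a database". Under Disseminating results: "A scientific publication of the results is planned". Under Protocol sequence, the final questionnaire comes after the eight weeks, and data processing comes after that.

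The design is one group of 50 with WOMAC completed twice. No withdrawal rate, authorisation rate, standard deviation or expected effect is given.

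**The concern.** In a single-group before-after study the result rests on the participants who supply both questionnaires. If people leave because the brace hurts or does not help, those who remain flatter it. The usual defence is to keep what leavers gave at baseline, compare it with the stayers' baseline, and perhaps bring it into the model. A rule that destroys those records by default seems to remove that defence for good, since no analysis plan can recover a destroyed record.

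The missing cut-off adds to the unease. Records stay coded, and so traceable, for five years, and a publication is planned. Read at its widest, the right to leave could produce a destruction request after the analysis, so that the archived data no longer match the published result.

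The fear, then, is a biased mean change that nobody can examine, and an archive that cannot reproduce it.

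**Working it through.** The Protocol states no figure to reproduce. The only document input is N = 50 ("50 adult participants will be recruited"); every other value below is an assumption.

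**1. Leaving before week 8: the primary comparison.** Let k leave, with s = 50 − k stayers. A leaver at this stage has no final WOMAC, so complete pairs = s whether the baseline is kept or not. For k = 2, 4, 10, s = 48, 46, 40. The completer mean is the same in every case. The missing change scores can bias the result: 10 missing scores with a 1 SD gap give (10/50) × 1 = 0.20 SD. That bias comes from the withdrawal, not from the destruction.

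**2. Leaving before week 8: the leaver-stayer comparison.** With m leavers' baselines kept, the 95% half-width in SD units is t(0.975, s + m − 2) × √(1/m + 1/s).

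| k | all kept | half kept | none kept |
|---|---|---|---|
| 2 | 1.45 | 2.03 | not possible |
| 4 | 1.05 | 1.45 | not possible |
| 10 | 0.71 | 0.96 | not possible |

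For k = 10 with all kept: 2.011 × √(1/10 + 1/40) = 2.011 × 0.354 = 0.71. Even with nothing destroyed, the comparison could not exclude a difference of most of an SD.

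**3. Leaving before week 8: a model that uses baseline-only records.** The mean change moves from the completer mean by (1 − b) × m/(s + m) × d in absolute size. Here d is the leavers' baseline difference and b the slope of final on baseline. Take d = 0.5 SD and b = 0.5.

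- All kept: 0.5 × (2/50) × 0.5 = 0.01; with 4/50, 0.02; with 10/50, 0.05 SD.
- Half kept: 0.5 × (1/49) × 0.5 = 0.005; with 2/48, 0.010; with 5/45, 0.028 SD.
- None kept: 0.
- For 10 kept, slopes of 0.3 and 0.7 give 0.07 and 0.03 SD.

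For scale, equal variances and slope 0.5 give a change SD of √(2 − 2 × 0.5) = 1. The standard error of the mean change is then 1/√48 = 0.144, 1/√46 = 0.147 and 1/√40 = 0.158. The shifts with everything kept are about 7%, 14% and 32% of one standard error. The Protocol does not mention such a model.

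**4. The anthropometry question.** The Protocol says of the measurements: "These data will be used in analyses to explore relationships with treatment efficacy". Relating anthropometry to efficacy needs a measured change. A leaver before week 8 has none, so that relation loses no observed pair either.

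**5. Leaving after the final questionnaire.** Only here does destruction remove a complete pair. Let stayers improve by 10 points and leavers by c, with k leaving and r authorising.

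- All-pairs mean = ((50 − k) × 10 + k × c)/50.
- Reported mean = ((50 − k) × 10 + r × c)/(50 − k + r).

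| reported minus all-pairs | c = −5 | c = 0 | c = 10 | c = 15 |
|---|---|---|---|---|
| k = 1, r = 0 | +0.3 | +0.2 | 0 | −0.1 |
| k = 2, r = 0 | +0.6 | +0.4 | 0 | −0.2 |
| k = 2, r = 1 | +0.29 | +0.20 | 0 | −0.10 |

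For k = 2, r = 0, c = −5: the all-pairs mean is (480 − 10)/50 = 9.4, against 10 reported.

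**6. The cut-off.** The right is to end participation, and the participant's tasks end with the final questionnaire. On an ordinary reading there is little left to end after that. The five-year coded period is a storage rule and grants no right of withdrawal. A destruction request after analysis needs the widest reading of the text.

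**The case for a change.** The strongest case for the concern is that destruction is fixed in the Protocol itself, so it cannot be left to an unseen analysis plan. Whatever method that plan names, it cannot use records that no longer exist. Keeping data needs a positive act from someone who is leaving and owes no explanation, so authorisation may be uncommon. The Protocol lists skin reactions, bruising and pain, which are plausible reasons to leave. The remedy would be cheap: a consent option and a sentence or two.

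Part of this stands. The loss is irreversible, the default is destruction, and no cut-off is written down.

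The rest does not make it a flaw. The Protocol does not link the listed harms to withdrawal, so the direction of any bias stays open. Reversing the default trades participants' control for data yield, a choice that belongs to the sponsor and the ethics committee. The consent form is not among the documents and may already ask for authorisation or set a limit. Participants who simply do not answer the e-mailed final questionnaire are untouched by the rule.

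**Conclusion.** The concern does not hold. The rule is stated once, with a trigger, a default and an exception, and nothing else in the Protocol contradicts it. For withdrawals before week 8 it leaves the complete pairs and their mean unchanged. What it can cost is a leaver-stayer comparison that is coarse even with full retention (half-width 0.71 to 1.45 SD), and a shift of about 0.01 to 0.05 SD at slope 0.5 (up to 0.07 SD at slope 0.3) in a model the Protocol does not mention. For withdrawals after the final questionnaire, the worst case worked above is 0.6 points on an assumed 10. It requires two non-authorising leavers who each did 15 points worse than the stayers.

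These sizes rest on assumed numbers of leavers, authorisation, timing, baseline difference, slope and improvement. The ranges include zero, and the effect on the reported mean can go either way. The unstated cut-off is a missing detail that the consent form may supply. A wish for a different default is a preference about consent policy, not a demonstrated fault in the design.
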